A Novel Telehealth Intervention using Nutrition and Exercise to Extend Intervention Benefits:
Enhancing Physical Function in the Long-term for Obese Older Adults

Pro 00105630

Version 1.0

4/24/2020

NCT04490356

Regulatory Sponsor: [name] [name]
Duke University
Department of Orthopaedic Surgery
[name]
[name]
[name]
[name]

Funding Sponsor: National Institutes of Health (NIH)

Study Summary

Title	A Novel Telehealth Intervention using Nutrition and Exercise to Extend Intervention Benefits: Enhancing Physical Function in the Long-term for Obese Older Adults
Short Title	Enhancing Physical Function in the Long-term for Obese Older Adults
Protocol Number	Pro00105630
Phase	N/A
Methodology	Qualitative individual interviews and/or focus groups will be conducted in-person or via the phone with: obese older adults who previously (within the last 20 months) participated in a weight loss intervention Single-arm pilot intervention investigating the feasibility, fidelity, and acceptability of a tele-nutrition and tele-exercise 3 month weight maintenance intervention
Study Duration	1 year
Study Center(s)	Single-center
Objectives	This study seeks to develop and test the feasibility, acceptability, and fidelity of a tele-nutrition and tele-physical activity weight-maintenance intervention tailored towards obese older adults who recently lost weight.
Number of Subjects	Up to 60 (Aim 1: up to 30; Aim 2: up to 20)
Diagnosis and Main Inclusion Criteria	Past participants of weight loss intervention for obese, older adults
Study Product, Dose, Route, Regimen	N/A
Duration of administration	N/A
Reference therapy	N/A
Statistical Methodology	We plan to use applied thematic analysis for the semi-structured interviews and focus groups. Descriptive statistics, proportions for feasibility, adherence and retention will be calculated, and student's t-test will be conducted to compare weight change over time in the pilot study.

1 Introduction

This document is a protocol for a human research study. This study is to be conducted according to US and international standards of Good Clinical Practice (FDA Title 21 part 312 and International Conference on Harmonization guidelines), applicable government regulations and Institutional research policies and procedures.

1.1 *Background*

[figure not shown]
The obesity pandemic, in combination with population aging, has created an urgent demand for effective treatments for geriatric obesity. Almost 40% of older (>60 years) adults in the U.S. are obese (BMI >30 kg/m²) (1) and similar trends are being recorded globally (2). Older adults with excessive body weights experience dramatic losses of mobility, independence, and performance of activities of daily living, as well as a host of metabolic and quality of life concerns (3-5). Yet, just as with other adult cohorts, obesity reduction presents a formidable challenge for older adults. In addition to their lower calorie requirements (due to decreased metabolic rate) and more sedentary lifestyles, older adults are prone to sarcopenia (loss of muscle mass and strength), which may be exacerbated by weight reduction. It is because of this concern that the advisability of obesity reduction in older adults has been called into question (6). However, there is increasing evidence that short-term weight loss can be safely achieved in this population (7), including our recent work showing improved function with enhanced protein intake during weight reduction (8).

The next step in evaluating the advisability of geriatric obesity treatment is to determine whether such benefits achieved during a period of relatively intense obesity treatment are retained over time, a so called “legacy effect”. A legacy effect has happened when the benefits from a treatment or intervention are shown to persist when the intervention is no longer being administered (put both references here instead of after next sentence). “Metabolic memory,” a related term, has been used to describe the long-term impact of intensive diabetes treatment (9, 10). The potential that a short-term treatment could yield long-term benefits could be especially promising for obese older adults, who often face a number of obesity-related comorbidities and may not be able to sustain the extra burden of an ongoing weight control regimen. Unfortunately, only two studies, to our knowledge, have explored the legacy effect of obesity reduction in older adults (11, 12), and only the study by Waters et al. (12) reported physical function outcomes. These investigators conducted an 18-month follow-up assessment in 16 frail, obese older subjects who had participated in a one year, single-armed weight loss plus exercise trial; they confirmed maintenance of benefits to body weight, physical function, insulin sensitivity, and other metabolic markers. Chmelo et al. (13), conducted an 18-month follow-up to a 5-month trial of resistance training (RT) versus resistance training plus caloric restriction (RT +CR), assessing body weight and composition as well as thigh composition but not physical function. They reported loss of thigh muscle mass in both groups and found weight regain and increased total fat mass in the RT +CR group.

While obesity interventions have been shown to provide dramatic functional benefits, the sustainability of these results over time and the net long-term impact on function is unknown.

Very recently (Figures 1 and 2 below; manuscript in preparation), we have shown a “legacy effect” of obesity treatment in this population; finding that the functional benefits of an intense period of intervention persist for a year or more, even if there has been weight regain. Given this exciting finding, we hypothesize that a practical, sustainable

telehealth intervention can be developed and implemented to magnify and extend these important legacy benefits. In the proposed research, we will 1) utilize experiences from the target population and experts in the field to develop a program of novel telehealth technologies to maintain and extend the legacy benefits of obesity treatment, and 2) evaluate the feasibility of this treatment in a pilot study of obese, functionally frail older adults.

2 Study Objectives

AIM 1a: In a series of semi-structured interviews with obese, functionally frail older adults who recently completed an intensive obesity intervention, we will collect key qualitative information on determinants (facilitators and barriers) of success in maintaining the functional benefits of obesity treatment over time. In ≥24 past weight loss intervention study completers (within 6 to 24months), we will conduct semi-structured interviews with 1) past participants who have maintained their weight loss and functional improvements, to identify personal beliefs, behaviors, and environmental factors that facilitated their success, and 2) past participants who have regained their weight, to identify personal beliefs, behaviors, and environmental factors leading to their treatment relapse.

AIM 1b: Utilizing results of Aim 1a, along with elements of our previously established evidence-based obesity intervention, we will develop a tele-nutrition and tele-exercise program intended to maintain and extend the benefits of a recent obesity intervention. Utilizing the information obtained from the semi-structured interviews and in consultation with experts in the area of telehealth, we will create a novel program of tele-nutrition and tele-exercise guided by the Social Cognitive Theory.³ The goal will be to maintain and extend the functional and quality of life benefits achieved in an intensive obesity intervention for older adults.

AIM 2: We will conduct a 3-month program of tele-nutrition and tele-exercise in 10 obese, functionally frail older adults who have successfully completed an obesity intervention (lost 5% of their body weight and increased SPPB by 1 point) and determine its feasibility, acceptability, and fidelity. Specifically, we will evaluate the feasibility (recruitment/retention)

[figure not shown]
of an intervention designed to extend legacy benefits, its acceptability (as assessed by attrition and participant satisfaction), and its fidelity (as assessed by adherence). Additionally, we will access physical function (SPPB) at 0 and 3 months.

3 Study Design

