8. What were your expectations of losing weight?
 - a) What were you hoping to change, achieve?
 - b) Were those expectations met? Not met?
9. Has COVID-19 impacted your nutrition and/or physical activity? If so, how? If not, why?

Environment

1. How does your family/friends influence your eating/exercise habits?
2. What do you feel are your main barriers to healthy eating/exercise?
3. How does your culture/community affect your eating/exercise habits?
4. While you were participating in the _____ study, where did your support come from?
5. When you were in the study how did your social support network (friends, family, colleagues) react?

AIM 1b: Develop novel, customizable tele-programs of nutrition and exercise to maintain and extend legacy benefits of a recent obesity intervention: Creation of tele-intervention protocols for testing

The information gained from the individual interventions, combined with our expertise in nutrition and exercise interventions in obese, frail older adults and our established experts in tele-health and behavior science will inform the content of Tele-nutrition and Tele-exercise Legacy Intervention. Furthermore, protocol development for the Legacy Intervention will employ Social Cognitive Theory³ components that are key to maintaining behavior change. Expected Findings: we anticipate the “Legacy Intervention” will include cognitive behavioral strategies (e.g., goal setting, self-monitoring, and social support) and draw upon a toolbox of e-approaches, including daily and weekly text reminders, virtual exercise classes, virtual individual and group nutrition classes, and step tracking device.

AIM 2: Determine the feasibility, acceptability, and fidelity of a 3-month lifestyle enhancing tele-intervention: Pilot intervention trial

The 3-month tele-nutrition and tele-physical activity intervention developed in Aim 1b will be pilot-tested in older adults who, within the last 3 months, successfully completed a lifestyle intervention and meet the inclusion criteria in Table 3.

Successful completion of a lifestyle intervention: lost at least 3% body weight and increased SPPB score by 1 point or increased their 6MWT by 50 meters from their baseline.

We will enroll participants until we reach a total of 10 study completers. We anticipate enrolling approximately 15, allowing for a 30% dropout rate.

Table 3. Inclusion/Exclusion Criteria Aim 2

Inclusion Criteria	Exclusion Criteria

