
 Participated in a weight loss intervention in the last 3 months and lost $\geq 3\%$ body weight and improved SPPB score by ≥ 1 point or 6MWT by ≥ 50 metes (Perera et al. J Am Geriatr Soc. 2006;54(5):743-9) Age ≥ 60 Able to speak and understand spoken and written English. Able to record dietary intake and weight 	
 Presence of unstable or symptomatic life-threatening illness Neurological conditions causing functional impairment, including Parkinson’s disease, multiple sclerosis, and permanent disability due to stroke Inability to complete physical function assessment No access to internet connection to participate in the tele-intervention Unable or unwilling to use provided tablet to participant in tele-intervention History of cognitive impairment

Setting: Screening will be conducted by telephone. Consents will be sent electronically and a consent presentation will be conducted virtually using Duke Zoom. Consented participants will come to the Duke Center for Living Stedman Center to receive their tablet and Garmin watch and will be provided an overview of how to login to the tele-intervention. All additional interaction will occur virtually.

Measurements:

Baseline: Baseline outcomes will be assessed after participant picks up tablet and Garmin watch. Using Duke Zoom, participants will be guided through their functional assessment and will be asked to complete their questionnaires using a REDcap link that was sent to them. Midpoint (6 weeks) and Endpoint (12 weeks): outcomes will be collected virtually as they were at baseline

Outcome Measures

Table 4: Aim 2 Outcome Measures and Collection Points

Measurement/Procedure	Time Points	Method
Function and Activity		
SPPB	0, 6, 12 weeks	Balance (side-by-side, semi-tandem, tandem), gait speed (3-meter timed walk), strength (chair stands).
6-minute walk test (aerobic endurance)	0, 6, 12 weeks	Farthest distance walked as possible in 6 minutes (measured using Garmin watch)
Average Step Count	Weekly	Average weekly step count will be determined using Garmin VivoSmart3 watch
Body Weight and Diet		
Body weight	Weekly	Same scale, light clothing and no shoes, measured to nearest 0.1 kg
3-day diet record; Daily food journal (Adherence)	0, 6, 12 weeks	3-day diet record by multiple pass; analyzed Food Processor (Version 10.13, 2013; ESHA Research); Daily food journal assessed by registered dietitian
Function, body composition		

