SPPB (6, 64, 66)	0, 6, 12 weeks	Balance (side-by-side, semi-tandem, tandem), gait speed (4-meter timed walk), strength (chair stands).
6-minute walk test (aerobic endurance)	0, 6, 12 weeks	As many walking laps as possible in six minutes between cones placed 40 meters apart
Questionnaires		
Quality of Life; Mood; Depression; Stress; Sleep; Life Satisfaction	0, 6, 12 weeks	SF-36; CES-D; Perceived stress; Pittsburgh sleep
Acceptability		
Participant Satisfaction Questionnaire	12 weeks	Participants will be asked to rate their satisfaction using a five point Likert scale (very dissatisfied; dissatisfied; neutral; satisfied; very satisfied) on a) satisfaction with the delivery of the tele-nutrition intervention, b) satisfaction with the delivery of the tele-exercise intervention c) satisfaction with their ability to maintain their physical function d) satisfaction with their ability to maintain their weight loss e) satisfaction with interactions with the registered dietitian.
Feedback Session	12 weeks	Using an interview guide we will examine aspects of the program in-depth from participants' perspectives.
Attrition Rate	12 weeks	Attrition Rate (%) = (Number of dropouts ÷ number of total participants) x 100
Feasibility		
Feasibility	12 weeks	Proportion of participants recruited will be calculated as the number of patients deemed potentially eligible and contacted for enrollment divided by the total number of patients enrolled.
Fidelity		
Adherence to tele-nutrition intervention	12 weeks	Proportion adherent to the tele-nutrition intervention will be computed by dividing the number of participants who maintained their weight by the total number of participants
Adherence to the tele-exercise intervention	12 weeks	Proportion adherent to the tele-exercise intervention will be computed by dividing the number of participants who maintained their functional status by the total number of participants
Retention	12 weeks	Proportion retention will be computed by dividing the number of retained subjects at the end of the intervention by the total number of participants

Risk/Benefit Assessment

The risk to human subjects for participation in this study is minimal compared to the potential health benefits they will receive from participating in the interventions and receiving detailed nutrition and exercise information.

Physical Risks:

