We will calculate these rates of retention, adherence, and attrition and their respective confidence intervals overall. While non-powerful, in a series of sensitivity tests, we will assess if adherence overall was impacted by demographic/socioeconomic variables.

We will employ a simplified applied thematic analysis for the feedback session recording and transcript following a similar approach to 1a above, less the NVivo interface and group comparison given the single group. Assessment of our measures used with screening/recruitment, adherence/retention, attrition/participant satisfaction, physical function, and self-efficacy will inform our feedback session interview guide where we will examine aspects of the program in-depth from participants' perspectives. This will allow us to examine individual level success through our objective intervention documentation in tandem with rich data from participants during the feedback session.

For physical function outcome measures a repeated measures analysis of variance will be employed to determine differences between timepoints, followed by pairwise comparison of each time point to the baseline time point.

7 Safety and Adverse Events

Oversight and Reporting: [name] will be responsible for the operation of this research study according to the study's protocol and IRB policies. Any serious adverse event, study-related or not study related will be reported via email to the Duke University IRB within 24 hours of learning about the event. Within 5 business days following the initial report, a Notification of a Problem or Event Requiring Prompt Reporting Form will be sent to the Duke IRB. This study is not an intervention and thus will not have a safety monitoring board, however the investigator will submit the number of adverse events, complaints, withdrawals, and protocol violations to the Duke University IRB. In addition, the PIs will review quarterly adverse event reports and make adjustments to the protocol if needed.

We expect adverse events to be limited to loss of protected health information. The study team has outlined procedures for data management to protect against loss of data (detailed below). Breaches in data security will be reported within 24 hours of detection, and a plan for management of the breach and modification of data security procedures will be developed within 3 business days, if applicable.

8 Data Handling and Record Keeping

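### The weight-change t-test stands only in the Study Summary; run as a paired week 0 to week 12 test, it would leave most weekly weights and about a third of those enrolled unused

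*Combined protocol and SAP*

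**What the plan says.** Under Statistical Methodology, the Study Summary states that a "student's t-test will be conducted to compare weight change over time in the pilot study". It does not give the time points, the pairing, the analysis set or the handling of missing weights.

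Section 6 presents itself as the analysis outline for both aims but has no analysis of mean weight change. Its only model for repeated outcomes is restricted to function: "For physical function outcome measures a repeated measures analysis of variance will be employed to determine differences between timepoints". Weight does enter through fidelity. Table 4 computes tele-nutrition adherence by "dividing the number of participants who maintained their weight by the total number of participants", and Section 6 gives adherence a confidence interval.

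On the data available:

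- Table 4 schedules body weight weekly: "Same scale, light clothing and no shoes, measured to nearest 0.1 kg".
- Follow-up runs to 12 weeks: "Midpoint (6 weeks) and Endpoint (12 weeks): outcomes will be collected virtually as they were at baseline".
- Section 5, Aim 2, sets enrolment: "We will enroll participants until we reach a total of 10 study completers" and "We anticipate enrolling approximately 15, allowing for a 30% dropout rate".
- Section 5, under Alternatives to Participation, keeps data gathered before withdrawal in use unless the participant asks in writing for their destruction. It also rules out further outcome collection after withdrawal.

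**The concern.** The programme is described as a weight-maintenance intervention, and its results are meant to inform a larger trial. The mean weight change over 12 weeks is therefore a figure that readers will carry forward, yet the analysis section does not say how it will be obtained.

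The usual way to run the summary's test is a paired comparison of week 0 with week 12. That needs a week-12 weight, which a withdrawn participant will not have. Such a test cannot use the earlier weights of people who left, so it sits badly with the commitment to use them. It also discards the intermediate weights of those who stayed.

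If leaving is related to regain, the mean among those who stay will look more stable than the mean among those who started. A non-significant result in about 10 people could then be mistaken for evidence of maintenance.

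**Working it through.** **1. The plan's own figure.** Ten completers with 30% dropout need 10/(1 − 0.30) = 14.3, rounded up to 15. This matches the stated enrolment. No power or sample-size figure is given for the weight test, so there is none to reproduce.

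**2. Data used by a paired week 0 to week 12 test.**

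- Weekly weights from week 0 to week 12 make 13 per completer. Two are used, so 11/13 = 85% are not. If one end of the series is not counted, 10/12 = 83% are not.
- With 10 completers among 15 enrolled, 5/15 = 33% are left out. At exactly 30% dropout the number is 4.5 of 15.

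**3. How far the completer mean can differ from the mean of all enrolled.** Suppose the 10 completers change by 0 kg on average and the 5 dropouts regain x kg. The mean of all enrolled is 5x/15. For x = 1, 2, 3 and 4 this gives 0.33, 0.67, 1.00 and 1.33 kg, while the completer test centres on 0.

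**4. What a paired test with n = 10 can show** (two-sided alpha of 0.05 assumed). The 95% half-width is 2.262/√10 = 0.72 SD of the change. Power is 29% for a true regain of 0.5 SD, and 80% power needs about 1.0 SD.

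**5. Simulation with dropout linked to observed regain.** The documents give no weight parameters, so all inputs are assumed: 15 enrolled; mean slope 0.10 kg per week, hence 12 × 0.10 = 1.2 kg true regain; slope SD 0.18; residual SD 0.6 kg; about 63 to 65% retained. The weekly log-odds of dropout rise by 0, 0.6 or 1.2 per kg regained. Each cell lists three separate simulations with the same or similar inputs. The values are mean estimated 12-week change in kg.

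| Link between regain and dropout | Completers only | Mixed model, all weekly weights |
|---|---|---|
| None | 1.16, 1.18, 1.13 | 1.22, 1.15, 1.25 |
| Moderate | 0.63, 0.53, 0.49 | 1.31, 1.36, 1.24 |
| Strong | 0.16, 0.03, −0.23 | 1.21, 1.38, 1.14 |

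Under the moderate link the completer mean falls short by 1.20 − 0.63 = 0.57 kg to 1.20 − 0.49 = 0.71 kg. The first simulation used 120 runs per scenario, so its completer means carry a Monte Carlo error of about 0.82/√120 = 0.07 kg.

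**6. Different inputs.** Here the true regain is 2.0 kg, the SD of 12-week change 2.0 kg, the measurement SD 0.7 kg, and about 76% complete. Completer means were 1.32, 1.39 and 1.58 kg across three dropout settings. In the middle case the mixed model gave 2.04 kg, and the completer shortfall was (2.0 − 1.39)/2.0 = 31%. With dropout unrelated to weight, the completer mean was 2.00 kg. With heavier dropout (57% completing), completers showed about 0.8 kg and the mixed model 2.2 kg.

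**7. Precision when dropout is unrelated to regain.** The empirical SD of the estimate was 0.82 kg for completers and 0.70 kg for the mixed model, a reduction of 1 − 0.70/0.82 = 15%. Repeats gave 10 to 17%. Each SD from 120 runs has about 6.5% Monte Carlo error, so this gain is modest and loosely estimated.

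**The case against.** Much of the case on the other side stands.

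- A reader might infer that the plan ignores weekly weights and excludes non-completers. It says neither. Both follow from one reading of an under-described test, and the withdrawal text points the other way.
- A reader might infer an unpaired test of week 0 against week 12. In a single-arm study, change over time naturally means within-person change, and a paired t-test is a Student's t-test. The documents give no reason to assume the unpaired version.
- A reader might infer that people who regain weight are the likeliest to leave. Nothing in the documents says so, and without that link the completer test is unbiased.
- A reader might infer that Section 6 does nothing with weight. It carries the adherence proportion, whose denominator is all participants. That proportion has no threshold for maintenance and no rule for people without a week-12 weight, so it does not replace an estimate of mean change.
- Mean weight change is not among the primary endpoints in Section 3.2. The study is a feasibility pilot, and attrition and retention are reported with intervals, so dropout stays visible. Reporting dropout does not, however, correct the weight estimate.
- The simulation inputs are assumed, and the data were generated with linear individual slopes, which is the form the mixed model fits. Its size should be read as illustrative.

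What remains is that the test is not carried into Section 6, and that its usual form wastes data the protocol collects and says it will use.

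**Conclusion.** The point holds as an inexpensive improvement to a secondary analysis, not as a fault that undermines the study. Section 6 lacks an analysis of mean weight change. A paired week 0 to week 12 test would use about 15% of the weekly weights (2 of 13) and about two thirds of those enrolled (10 of 15).

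Under a moderate link between regain and dropout, the completer mean understated a true 1.2 kg regain by roughly half. With other assumed inputs the shortfall was about 30%, and with no link there was none. The direction of the bias is conditional on that link, and its size depends on assumed values.

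The mixed model stayed near the truth where dropout depended on observed weights. It would not be protected if dropout depended on weights never recorded. Whichever test is used, with about 10 completers a non-significant result cannot establish that weight was maintained.

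**What to change.** Replace the t-test sentence in the Study Summary with a reference to Section 6, and add there a paragraph to this effect:

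*Mean change in body weight from week 0 to week 12 will be estimated with a 95% confidence interval from a linear mixed model fitted to all weekly weights of all enrolled participants, with a random intercept and slope and a small-sample degrees-of-freedom method. A paired t-test of week 0 against week 12 in completers will be supportive. A sensitivity analysis will assume additional regain after the last recorded weight in participants who dropped out. A non-significant result will not be interpreted as maintenance of weight.*

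The sensitivity analysis can be simple: with 5 dropouts among 15 enrolled, each extra 1 kg assumed in dropouts moves the overall mean by 5/15 = 0.33 kg. Weights that a participant has asked in writing to have destroyed would be excluded, as the protocol already provides.

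The cost is protocol wording and slightly more analysis work, with no new measurements. The model assumes roughly linear change over 12 weeks and dropout that depends only on observed weights. Both assumptions should be stated, and the first can be checked by plotting the weekly series.
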